10.3.2 Treatment Exposure

Duration of exposure will be calculated for each subject as (last dose date – first dose date + 1) and will be summarized using descriptive statistics. The number of subjects who receive ≥ 1 day, ≥ 7 days, ≥ 14 days, ≥ 28 days, ≥ 42 days, ≥ 56 days, ≥ 70 days, and ≥ 84 days of the study medication will be presented by actual treatment group for the SAS.

Days on treatment will be computed as the number of days that the study medication was taken (ie, treatment exposure excluding days when the study medication was interrupted). Number of days on treatment and number of days study medication was interrupted for will be summarized for the SAS.

11 EFFICACY PARAMETERS

11.1 Primary Analysis

The primary efficacy endpoint (percent CFBL to Week 12 in LDL-C) will be analyzed using ANCOVA and the FAS population. The null hypothesis to be tested is that there is no difference in the expected percent CFBL to Week 12 in LDL-C between the active treatment (subjects treated with gemcabene 600 mg) and placebo (subjects treated with placebo) groups after adjusting for baseline statin-intensity stratum, baseline diabetes status, and baseline LDL-C. Explicitly, in the ANCOVA, percent CFBL to Week 12 in LDL-C will be the dependent variable whereas randomized treatment group (gemcabene 600 mg or placebo), baseline statin-intensity stratum (moderate or high), and baseline diabetes status (yes or no) will be included as factors, and baseline LDL-C will be included as a covariate. LOCF will be used to impute missing values for Week 12; only post-baseline values will be used for imputation. The least-squares mean (LSM) and standard error (SE) for percent CFBL to Week 12 in LDL-C for each treatment group and the least-squares mean and 95% confidence interval (CI) of the treatment difference will be produced from the model using type III sums of squares to estimate the magnitude of the treatment effect. The following SAS code will be used to conduct the ANCOVA:

```
proc glm data=data;  
  class Drug(ref="Placebo") Diabetes StatinStrat;  
  model pctCFBL = Drug Diabetes StatinStrat Base / solution;  
  lsmeans Drug / stderr pdiff out=adjmeans;  
run;
```

The following additional analyses will be performed to assess assumptions of ANCOVA. The assumptions of normality and homoscedasticity (equal variance) will be assessed using residuals from the ANCOVA. Explicitly, normality will be assessed by visually inspecting quantile-quantile plots and conducting the Shapiro-Wilk test. If normality is clearly violated, ranked ANCOVA will be conducted. Further, Levene's test will be conducted and residual plots will be visually assessed to determine if the assumption of homoscedasticity is met. Lastly, we will investigate the assumption of homogeneity of regression slopes across treatment groups (parallel slopes) by including the interaction between baseline LDL-C and treatment group in the model explicated previously. If results indicate that the interaction between baseline LDL-C and treatment group is not significant, we will assume that the assumption of parallel slopes is met. If the assumption of homoscedasticity or parallel slopes is clearly violated, the final model may be adjusted.

Confirmatory analysis will be conducted by performing the primary analysis using the PPS population.

11.2 Secondary Analysis

All secondary analyses will be conducted using the FAS population (or the specific subgroup within the FAS population, eg, diabetic subjects) with subjects included in their randomized treatment group regardless of the treatment they actually received.

Similar analysis of ANCOVA as specified for the primary analysis in the above section will be conducted for the secondary efficacy endpoints. Note that the covariate included in the ANCOVA will be the baseline value of the parameter of interest (eg, if the parameter of interest is HDL-C, the covariate in the ANCOVA will be HDL-C at baseline).

As previous research suggests that hsCRP and TG are non-normally distributed,^{3,4,5} hsCRP and TG will be analyzed using ranked ANCOVA.⁶ Results of parametric ANCOVA will also be provided for these parameters as supportive results. Ranked ANCOVA will be conducted by first ranking the outcome and covariate at a given timepoint (eg, Week 12) prior to conducting ANCOVA. The p-value corresponding to the difference in ranked outcome between treatment groups will be output, and results will be interpreted in the context of the median change from baseline for each treatment group. The SAS code for conducting ranked ANCOVA is provided below (this can be extended to percent change from baseline):

```
proc rank data=data out=data_rank ties=mean;
    var base chg;
    ranks r_base r_chg;
run;

proc glm data=data_rank;
    class Drug(ref="Placebo") Diabetes StatinStrat;
    model r_chg = Drug Diabetes StatinStrat r_base / solution;
    lsmeans Drug / stderr pdiff cl out=adjmeans;
quit;
```

The secondary efficacy endpoints that are binary will be analyzed using logistic regression. The output from each logistic regression model will include the odds ratio (OR), 95% CI, and the associated p-value. The SAS code for conducting a logistic regression model is provided below:

```
proc logistic data=data;
    class Drug(ref="Placebo") Diabetes StatinStrat;
    model Outcome(event="event") = Drug Diabetes StatinStrat Base / expb;
run;
```

The secondary efficacy analyses are:

- percent CFBL to Week 12 in LDL-C within each statin-intensity stratum (moderate, high);
- CFBL to Weeks 2, 4, 8, and 12 in LDL-C;
- percent CFBL to Weeks 2, 4, and 8 in LDL-C;
- CFBL and percent CFBL to the average of Weeks 8 and 12 in LDL-C;
- CFBL and percent CFBL to Weeks 2, 4, 8, and 12 in non-HDL-C, TC, TG, HDL-C, and VLDL-C;
- percent of subjects achieving a LDL-C reduction of $\geq 10\%$, $\geq 15\%$, and $\geq 20\%$ at Weeks 4, 8, and 12 (separately);
- percent of subjects achieving a LDL-C value < 100 mg/dL (2.59 mmol/L) at Weeks 4, 8, and 12 (separately);

- CFBL and percent CFBL to Weeks 4, 8 and 12 in ApoB, ApoA-I, ApoA-II, ApoA-V, ApoC-II, ApoC-III, ApoE, and Lp(a);
- CFBL and percent CFBL to Week 12 in hsCRP, SAA, adiponectin, and fibrinogen; and
- CFBL to Week 12 in Framingham Risk Score.

Percent CFBL to Week 12 in LDL-C within each statin-intensity stratum (moderate and high) will be analyzed using the same approach as the primary analysis except that baseline statin-intensity stratum will not be included in the model.

CFBL to Weeks 2, 4, 8, and 12 in LDL-C, percent CFBL to Weeks 2, 4, and 8 in LDL-C, and CFBL and percent CFBL to the average of Weeks 8 and 12 in LDL-C will be analyzed using the same approach as the primary analysis.

CFBL and percent CFBL to Weeks 2, 4, 8, and 12 in non-HDL-C, TC, TG, HDL-C, and VLDL-C, CFBL and percent CFBL to Weeks 4, 8 and 12 in ApoB, ApoA-I, ApoA-II, ApoA-V, ApoC-II, ApoC-III, ApoE, and Lp(a), and CFBL and percent CFBL to Week 12 in hsCRP, SAA, adiponectin, and fibrinogen will be analyzed using the same approach as the primary analysis, except that hsCRP and TG will be analyzed with ranked ANCOVA.

Percent of subjects achieving an LDL-C reduction of $\geq 10\%$, $\geq 15\%$, and $\geq 20\%$ at Weeks 4, 8, and 12 (compared to baseline), and percent of subjects achieving an LDL-C value < 100 mg/dL (2.59 mmol/L) at Weeks 4, 8, and 12 (compared to baseline) will be analyzed using logistic regression. Explicitly, we will estimate the odds of achieving the corresponding reduction (ie, $\geq 10\%$, $\geq 15\%$, and $\geq 20\%$) or an LDL-C value < 100 mg/dL at a given week using logistic regression. Randomized treatment group (gemcabene 600 mg or placebo), baseline statin-intensity stratum (moderate- or high-intensity), diabetes status (yes or no), and baseline LDL-C will be included in each model as factors.

Framingham Risk Score at baseline and Week 12 along with CFBL in Framingham Risk Score to Week 12 will be summarized by randomized treatment group using descriptive statistics. Framingham Risk Score at baseline has been explicated previously. Framingham Risk Score at Week 12 will be computed for each subject using the following variables at the following time points: age at the Screening Visit, TC at Week 12, HDL-C at Week 12, SBP at Week 12, treatment for hypertension at Week 12, smoking status at Day 1, and diabetes status at the Screening Visit. A subject is considered to be receiving treatment for hypertension at Week 12 if there is at least one treatment for hypertension with a start date on or before their Week 12 Visit (last dose) (ie, medication start date \leq day of last dose) and a stop date on or after their Week 12 Visit (last dose) (ie, medication stop date \geq day of last dose). Partial and missing dates will be imputed using rules in [Appendix 2](#).

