2.2 Secondary Objectives

The secondary objectives of this study are the following:

- To assess the LDL-C lowering of gemcabene 600 mg in (1) subjects on high-intensity statin therapy; and (2) subjects on moderate-intensity stable statin therapy treated for 12 weeks.
- To assess the safety and tolerability of gemcabene 600 mg in all subjects combined and separately in (1) subjects on high-intensity statin therapy; and (2) subjects on moderate-intensity stable statin therapy treated for 12 weeks.
- To assess the effect of gemcabene on other lipid and apolipoprotein parameters, hsCRP, adiponectin, fibrinogen, and cardiovascular risk over 12 weeks of treatment.

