For continuous secondary and exploratory efficacy endpoints related to change/percent change in basic fasting lipids, lipoproteins, hsCRP, SAA, fibrinogen, adiponectin, FPG, fasting insulin and **CI** [REDACTED] the same ANCOVA for the primary efficacy endpoint will be used, with the respective baseline included as the covariate. Note that for secondary endpoints such as change from baseline in LDL-C within the moderate-intensity stratum, the ANCOVA model will not include a term for baseline statin intensity stratum. Baseline for TC, non-HDL-C, HDL-C and VLDL-C are defined similarly to baseline for LDL-C. Baseline for fasting lipoproteins, hsCRP, SAA, fibrinogen, adiponectin, FPG, fasting insulin and serum **CI** [REDACTED] are defined as the value from pre-dose Day 1/Visit T1. Baseline for HbA1c is the value from the first visit (Pre-Screening or Screening Visit).

Each ANCOVA will be performed using the FAS (or the specific subgroup within the FAS that is indicated in the specific endpoint [e.g. subgroup of baseline high-intensity statin subjects]), with subjects included in their randomized treatment group regardless of the treatment they actually received. Missing values for post-randomization time points will be imputed using LOCF; only post-baseline values will be used for the imputation. The output from each ANCOVA will include the LSM and SE for both treatment groups, along with the placebo-corrected LSM, its 95% CI and associated p-value. For every continuous endpoint (each parameter, each time point), if non-normality is detected, then either the data will be transformed so that it is normally distributed or a nonparametric test will be used.

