The percent of subjects achieving LDL-C reduction of $\geq 10\%$, $\geq 15\%$ and $\geq 20\%$ at Week 4, Week 8, and Week 12 will each be analyzed using a logistic regression with treatment, baseline statin intensity (high-intensity; moderate-intensity), baseline diabetes (Y/N) and baseline LDL-C value as independent factors. For each analysis, the percent of subjects in each treatment group meeting the criteria, the odds ratios with 95% CI, and p-value will be provided. The percent of subjects achieving a LDL-C value <100 mg/dL (2.59 mmol/L) at Week 4, Week 8, and Week 12 will be analyzed in the same manner, with similar output provided for each endpoint. For all of these endpoints, the FAS will be used, with subjects included in their randomized treatment group regardless of the treatment they actually received.

Framingham Risk scores and estimated 10-year risk will be summarized at baseline and Week 12. Additionally, the change from baseline to Week 12 in Framingham Risk scores and estimated 10-year risk will be summarized. The number and percent of subjects in each NCEP ATP-III Risk category will be summarized at baseline and Week 12. Also, a shift table of NCEP ATP-III Risk categories from baseline and Week 12 will be provided. The FAS, with subjects included in their randomized treatment group regardless of the treatment they actually received, will be used for all of these summarizations. Finally, ^C

Confirmatory analysis of the secondary and exploratory endpoints will be performed using the PPS.

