5.2 Secondary Objectives

The secondary objectives of this study are the following:

- to assess the LDL-C lowering of gemcabene 600 mg in (1) subjects on high-intensity stable statin therapy; and (2) subjects on moderate-intensity stable statin therapy treated for 12 weeks;
- to assess the safety and tolerability of gemcabene 600 mg in all subjects combined and separately in (1) subjects on high-intensity stable statin therapy; and (2) subjects on moderate-intensity stable statin therapy treated for 12 weeks; and
- to assess the effect of gemcabene on other lipid and apolipoprotein (Apo) parameters, high-sensitivity C-reactive protein (hsCRP), serum amyloid A (SAA), adiponectin, fibrinogen, and cardiovascular risk over 12 weeks of treatment.

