6.2 Efficacy Measures

The primary efficacy measure is the percent change from baseline (CFBL) to Week 12 in fasting LDL-C (hereafter referred to as “LDL-C”).

The secondary efficacy measures are:

- percent CFBL to Week 12 in LDL-C within each statin-intensity stratum (moderate, high);
- CFBL and percent CFBL to Weeks 2, 4, 8, and 12 in LDL-C;
- CFBL and percent CFBL to the average of Weeks 8 and 12 in LDL-C;
- CFBL and percent CFBL to Weeks 2, 4, 8, and 12 in non-high-density lipoprotein cholesterol (non-HDL-C), total cholesterol (TC), TG, HDL-C, and very low-density lipoprotein cholesterol (VLDL-C);
- percent of subjects achieving a LDL-C reduction from baseline of $\geq 10\%$, $\geq 15\%$, and $\geq 20\%$ at Weeks 4, 8, and 12;
- percent of subjects achieving a LDL-C value < 100 mg/dL (2.59 mmol/L) at Weeks 4, 8, and 12;
- CFBL and percent CFBL to Weeks 4, 8 and 12 in ApoB , ApoA-I, ApoA-II, ApoA-V, ApoC-II, ApoC-III, ApoE, and lipoprotein(a) (Lp[a]);
- CFBL and percent CFBL to Week 12 in hsCRP, SAA, adiponectin, and fibrinogen; and
- CFBL to Week 12 in Framingham Risk Score (ie, 10-year risk of developing cardiovascular disease [CVD]).

The exploratory efficacy measures are:

C [REDACTED]

[REDACTED]

[REDACTED]

[REDACTED]

[REDACTED]

[REDACTED]

- **CI** [REDACTED]

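### Change in Framingham Risk Score, the only remaining secondary measure of cardiovascular risk, is the one continuous secondary endpoint with no planned adjusted comparison with placebo

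*SAP*

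**What the plan says.** Both documents include cardiovascular risk in a secondary objective about the effect of gemcabene. SAP 5.2 lists "adiponectin, fibrinogen, and cardiovascular risk over 12 weeks of treatment", and Protocol 2.2 lists "hsCRP, adiponectin, fibrinogen, and cardiovascular risk over 12 weeks of treatment".

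Change to Week 12 in Framingham Risk Score is a secondary endpoint in Protocol 9.3.1.2 and in SAP 6.2 and 11.2. The protocol's other risk endpoint, NCEP ATP-III risk, is dropped in SAP 8 because the CRFs did not collect family history of premature coronary heart disease.

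The general analysis rules point to a model. SAP 11.2 opens with "Similar analysis of ANCOVA as specified for the primary analysis in the above section will be conducted for the secondary efficacy endpoints". SAP 9.2 says that secondary and exploratory analyses follow an approach similar to the primary ANCOVA, with logistic regression when the outcome is binary.

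The endpoint-specific rule points elsewhere. SAP 11.2 says "CFBL in Framingham Risk Score to Week 12 will be summarized by randomized treatment group using descriptive statistics". Under SAP 9.2, summaries of a continuous variable are the mean, SD, median, minimum and maximum. Protocol 9.3.1.2 likewise says that "the change from baseline to Week 12 in Framingham Risk scores and estimated 10-year risk will be summarized".

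**The concern.** An objective about the effect of a drug in a placebo-controlled trial is answered by a between-arm contrast with a measure of its uncertainty. For cardiovascular risk the plan stops at two columns of summary statistics. Every other continuous secondary endpoint gets an ANCOVA, or a ranked ANCOVA with a parametric ANCOVA in support. No reason is given for treating this one differently.

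The SAP can also be read in two ways. A programmer who follows SAP 9.2 and the opening of 11.2 would fit a model. One who follows the later Framingham paragraph would not. What is at stake is the reported answer to one part of one secondary objective.

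**Working it through.** **The passages side by side**

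| Place | What it gives change in Framingham score |
|---|---|
| SAP 9.2 | Continuous, so an ANCOVA-type analysis by the general rule |
| SAP 11.2, opening | ANCOVA, as for the secondary endpoints in general |
| SAP 11.2, endpoint list | Included as a secondary analysis |
| SAP 11.2, paragraphs assigning the primary approach | Not named; LDL-C, other lipids, apolipoproteins and inflammatory markers are |
| SAP 11.2, Framingham paragraph | Descriptive statistics by arm |
| Protocol 9.3.1.2, ANCOVA paragraph | Not named in the visible list, which starts "For continuous secondary and exploratory efficacy endpoints related to change/percent change in basic fasting lipids, lipoproteins, hsCRP, SAA, fibrinogen, adiponectin, FPG, fasting insulin and" and continues into redacted text |
| Protocol 9.3.1.2, Framingham paragraph | Summarized |
| Protocol 9.3.1.2, multiplicity text | Each secondary endpoint is compared with the 0.05 level, which implies a test, but none is specified |

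The specific paragraph is the better guide to what would be run, and it agrees with the protocol. It still contradicts the two general SAP statements, neither of which exempts Framingham.

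**The plan's own figure**

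No figure is stated for this endpoint. The LDL-C sample size reproduces: for a difference of 17 and SD 20 with a two-sided 0.05 t-test, 23 evaluable subjects per arm per stratum give 80.5% power. Then 23/0.9 = 25.6, rounded up to 26, and 26 × 2 arms × 2 strata = 104. The point does not depend on this.

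**What an ANCOVA would deliver at the planned size**

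Inputs: 52 randomized per arm (SAP 9.1). With 10% drop-out, 52 × 0.9 = 46.8, taken down to 46. The model has five parameters (intercept, treatment, statin stratum, diabetes, baseline score), so df = 2n − 5. The residual SD is not in the documents; 2, 3 and 5 percentage points of 10-year risk are assumed.

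95% CI half-width = t(0.975, 2n − 5) × SD × √(2/n)

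| n per arm | df | Half-width in SD units | SD 2 | SD 3 | SD 5 |
|---|---|---|---|---|---|
| 52 | 99 | 0.389 | 0.78 | 1.17 | 1.95 |
| 46 | 87 | 0.414 | 0.83 | 1.24 | 2.07 |

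The range is therefore about 0.8 to 2.1 points.

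**What a reader could derive without the model**

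The arm means, SDs and Ns give a crude difference. Its half-width with equal SDs is t(0.975, 2n − 2) × SD × √(2/n), which is 0.389 SD at 52 per arm and 0.414 SD at 46. The multipliers are the same to three decimals, so adjustment gains precision only by making the residual SD smaller than the raw SD. The factor is √(1 − R²), where R is the multiple correlation of change with the covariates. R is not given either. At assumed values of 0.3 and 0.5 the interval narrows by about 5% (√0.91 = 0.954) and 13% (√0.75 = 0.866).

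**The case against.** The strongest reply is that this is a prespecified choice and not an oversight. The protocol synopsis, Protocol 9.3.1.2 and SAP 11.2 all say that Framingham is summarized, and a specific rule governs a general one. On that view one exempting clause cures the conflict. Consistency across the documents does show intent. It does not make a by-arm summary answer an objective about the drug's effect.

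Several other points on that side stand and limit the concern:

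- A reader might infer that the trial would yield no treatment effect or interval for cardiovascular risk. The documents do not support that. Means and SDs by randomized arm are planned, so a crude difference and its CI can be derived, and under 1:1 stratified randomization that difference is not biased by baseline risk. Only the planned, adjusted and reported estimate is missing.
- A reader might also infer that falls within each arm, partly regression to the mean, would be taken for drug effect. Regression to the mean is expected equally in both randomized arms, placebo is shown beside gemcabene, and no within-arm test is planned.
- Much of the content is modelled already. Age, smoking and diabetes are fixed at Screening or Day 1, so only total cholesterol, HDL-C, systolic pressure and hypertension treatment can move the score. Both lipids get ANCOVA, and systolic pressure is summarized by arm (SAP 12.4).
- The score estimates the risk of developing cardiovascular disease, including myocardial infarction (SAP 6.2). The trial admits subjects with ASCVD, documented by prior infarction, stenosis or revascularization (Protocol 6.3). In them the score is hard to interpret, and a confidence interval does not change that.
- A log-transformed analysis reported as a ratio may look attractive for a risk score. The documents give no distribution for it, the stated endpoint is change in the score, and the SAP already has a rule for non-normality.

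**Conclusion.** The point holds as a cheap improvement. The SAP contradicts itself on how change in Framingham Risk Score is analysed. The rule most likely to be followed leaves the last secondary measure of cardiovascular risk as the only continuous secondary endpoint without a planned, covariate-adjusted placebo contrast.

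In size, the existing ANCOVA would give a 95% CI of about ±0.39 to ±0.41 residual SD. The conversion to 0.8 to 2.1 risk points rests wholly on an assumed SD of 2 to 5 and on 46 to 52 analysed subjects per arm. The documents name no meaningful difference in the score, so these figures describe precision and do not show that any conclusion would change.

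Secondary p-values are descriptive under both documents. The primary LDL-C analysis and its power are untouched.

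**What to change.** In the Framingham paragraph of SAP 11.2, state that change from baseline to Week 12 in Framingham Risk Score will be analysed in the FAS with the ANCOVA already specified: treatment, statin-intensity stratum and diabetes status as factors, and baseline score as covariate. Report the least-squares mean difference from placebo with its 95% CI. If normality is clearly violated, apply the ranked ANCOVA that SAP 11.1 already provides. Keep the descriptive table. The paragraph then agrees with SAP 9.2 and the opening of 11.2.

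The cost is a sentence or two and one model run on scores already computed, with no new subjects or data. It adds one more unadjusted, descriptive p-value. The report should say that the score is harder to interpret in subjects who already have ASCVD.

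If the sponsor prefers to keep the descriptive rule, SAP 9.2 and 11.2 should exempt Framingham by name. That removes the contradiction but leaves this part of the objective without an adjusted estimate.

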11.3 Exploratory Analysis

CI

CI [REDACTED]

[REDACTED]

[REDACTED]

[REDACTED]

[REDACTED]

[REDACTED]

[REDACTED]

[REDACTED]

[REDACTED]

11.4 Manuscript Analysis

Please refer to [Appendix 5](#). for additional analyses that will be performed for inclusion in a manuscript. Further, please note that results of these analyses will not be presented in the clinical study report.

